### **6.5.2 Multiplicity among multiple evaluations**

Stable platelet response is set as the primary endpoint and other variables will be used for reference only. Therefore, multiplicity adjustment among multiple variables will not be performed.

### **6.5.3 Multiplicity for multiple analysis sets**

Not applicable because only the FAS, SS, and PKS will be used for the analysis of efficacy, safety, and pharmacokinetics, respectively.

## **6.6 Use of an “Efficacy Subset” of Subjects**

Not applicable because only the FAS will be used for efficacy analysis.

## **6.7 Active-Control Studies Intended to Show Non-inferiority**

Not applicable.

## **6.8 Subgroup Analyses**

Efficacy will be analyzed for each line of therapy and by stable platelet response. For details, see “[11.3 Subgroup Analysis of Efficacy](#).” No subgroup analysis of safety will be performed.

## **7. Definition of Derived Data**

Each variable will be calculated based on the following definitions.

- The following drugs are considered as prior ITP medications:

- Drugs collected as prior ITP medications
- Drugs collected as permitted concomitant ITP medications that were used prior to study drug administration
- Number of unique prior ITP medications (categories)  
Defined as the number of categories of prior ITP medications used. For example, if 3 corticosteroids and rituximab are used, the number of prior ITP medications (categories) will be 2.
- Number of unique prior ITP medications (drugs)  
Defined as the number of prior ITP medications used. For example, if eltrombopag olamine and romiplostim are used, the number of prior ITP medications will be 2.
- Line of therapy  
Prior ITP medications will be classified into the following line of therapy categories. The line of therapy will be the number obtained by adding 1 to the number of categories (excluding “Other”). For category “Other,” the number of generic names of the relevant medications will be added to the line number. If splenectomy was performed, add 1 to the line number. However, if prior ITP medications only include steroid (“Corticosteroids” or “Danazol”) and/or “Intravenous Immunoglobulins” and splenectomy has not been performed, the line of therapy will be 2 instead of 3.
  - Line of therapy categories: Thrombopoietin Receptor Agonists, Corticosteroids, Intravenous Immunoglobulins, Rituximab, Immunosuppressant, Danazol, Chemotherapy, Other.
- Duration of exposure
  - Period I: Day of last administration in Period I – Day of first administration in Period I + 1
  - Long-term treatment of R788
    - For subjects who discontinued Period I: Day of last administration in Period I – Day of first administration in Period I + 1
    - For subjects who completed Period I and transitioned to Period II: Day of last administration in Period II – Day of first administration in Period I + 1
  - Period II: Day of last administration in Period II – Day of first administration in Period II + 1
  - Non-dosing period: End day of the non-dosing period – Start day of the non-dosing period + 1
  - Period III: Day of last administration in Period III – Day of first administration in Period III + 1
  - R788 treatment period: Day of last administration of R788 – Day of first administration of R788 + 1 – (End day of the non-dosing period – Start day of the non-dosing period)
- Elapsed time after administration = Time of blood sampling – Time of study drug administration
- Treatment compliance = Total number of administered tablets / Number of prescribed tablets × 100

- Number of prescribed tablets

Defined as the sum of the products of the number of tablets prescribed per day and the duration of treatment. However, if dose interruption due to an AE or any other reasons occurs during a period other than the non-dosing period, the dose prescribed immediately before the dose interruption will be applied.

- Treatment dose at each analysis visit

Defined as the dose at the time of measurement of platelet count. For Day 1 of Period I, Week 24 of Period II, and Day 1 of Period III, the initial doses for each period will be used. If the study drug is interrupted on the relevant day, the dose will be categorized as interruption. Analysis visits after treatment discontinuation will be excluded from the analysis.

- Average daily dose

Defined as the weighted average of treatment dose, with the duration of exposure at each dose as the weighting factor. Dose interruption will be handled as 0 mg dose.

- Duration of platelet response = End day of response – Start day of response + 1

The start day of response is defined as the first day after the start of study treatment in each period on which a platelet count of  $\geq 50000/\mu\text{L}$  for at least 28 consecutive days without the use of rescue medications was achieved. The end day of response is defined as the day of use of a rescue medication or the first day of the period in which the platelet count fell below  $50000/\mu\text{L}$  for at least 28 consecutive days, whichever is earlier. For subjects who discontinue or complete each period with the platelet count maintained at  $\geq 50000/\mu\text{L}$ , the last measurement day in each period is defined as the end day of response. The calculation of the duration of platelet response includes analysis visits outside the acceptable time window and unscheduled visits.

- Sustained stable platelet response

Subjects who achieve a platelet count of  $\geq 50000/\mu\text{L}$  within 12 weeks after the start of study treatment and maintain it for the subsequent 12 weeks will be considered as responders. Maintenance of the platelet count for the subsequent 12 weeks is defined as platelet response for at least 12 weeks (85 days). All subjects not assessed as responders due to discontinuation or missing data will be considered as non-responders.

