8.2 Structure of the Study

1) Screening period

Screening period is defined as 4 weeks from Screening A to before the administration of the study drug on Day 1.

2) Period I

Period I is defined as 24 weeks from after the administration of the study drug on Day 1 to Week 24.

3) Period II

- The day at the beginning of study drug administration in Period II is Week 24 for subjects who complete Period I. Period II is defined as 28 weeks from Weeks 24 to 52.
- The day at the beginning of study drug administration in Period II is ET Day 1 for early transition subjects. Period II is defined as 28 weeks from ET Day 1 to ET Week 28.

4) Non-dosing period

Non-dosing period is defined as maximum 4 weeks from Week 52 or ET Week 28 to Day 1 of Period III.

5) Period III

Period III is defined as the period from Day 1 of Period III to the date of marketing approval of R788.

6) Follow-up period

- Follow-up period is defined as 2 weeks from Week 52 or ET Week 28 to the tests at the end of the follow-up period for subjects who complete Period II and are not willing to participate in the Non-dosing period and Period III.
- Follow-up period is defined as 2 weeks from the Withdrawal Visit to the tests at the end of the follow-up period for subjects who withdraw from Period I and do not transition to Period II, those who withdraw from Period III.
- Follow-up period is defined as the period until 2 weeks after Week 52 or ET Week

28 for subjects who withdraw from the Non-dosing period before ND Week 2.

• No follow-up period is established for subjects who withdraw from the Non-dosing period at ND Week 2 or later or subjects who continue Period III until the date of marketing approval of R788.

[figure not shown]

Figure 8.2-1 Structure of Study

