## 6) Evaluation in R788 treatment period

Day 1 of the R788 treatment period is defined as the first day of study drug administration in Period I for subjects who received R788 in Period I, and as the first day of study drug administration in Period II for those who received placebo in Period I and transitioned to Period II. No analysis visit-specific analysis will be performed for evaluation in the R788 treatment period.

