## **10.2 Distribution of Duration of Exposure**

Applicable period: Period I, long-term treatment of R788, Period II, non-dosing period, Period III, and R788 treatment period

The variables to be analyzed are as follows:

- Duration of treatment (Period I):  $<4$ ,  $4 \leq <8$ ,  $8 \leq <12$ ,  $\geq 12$  weeks
- Duration of treatment (long-term treatment of R788):  $<4$ ,  $4 \leq <8$ ,  $8 \leq <12$ ,  $12 \leq <24$ ,  $\geq 24$  weeks

- Duration of treatment (Period II):  $<4$ ,  $4 \leq <8$ ,  $8 \leq <12$ ,  $12 \leq <24$ ,  $\geq 24$  weeks
- Duration of dose interruption (non-dosing period):  $<4$ ,  $\geq 4$  weeks
- Duration of treatment (Period III):  $<24$ ,  $24 \leq <48$ ,  $48 \leq <72$ ,  $\geq 72$  weeks
- Duration of treatment (R788 treatment period):  $<4$ ,  $4 \leq <8$ ,  $8 \leq <12$ ,  $12 \leq <24$ ,  $24 \leq <52$ ,  $\geq 52$  weeks

The numbers and percentages of subjects will be presented. The duration of dose interruption will be presented for the non-dosing period.

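### The R788-treatment-period exposure formula subtracts the Non-dosing period even when R788 was not restarted, so it removes on-drug days for subjects who withdraw during that period

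*SAP*

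**What the plan says.** SAP section 7 lists one exposure formula per evaluation period. For the R788 treatment period it takes the day of last R788 administration minus the day of "first administration of R788 + 1 – (End day of the non-dosing period – Start day of the non-dosing period". No condition is attached.

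Two neighbouring formulas cover the same doses for some subjects and subtract nothing:

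- Period II: "Period II: Day of last administration in Period II – Day of first administration in Period II + 1".
- Long-term treatment, for R788 subjects who completed Period I and went on to Period II: "Day of last administration in Period II – Day of first administration in Period I + 1".

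For Period I placebo subjects, SAP 5.9 item 6 sets Day 1 of the R788 treatment period "as the first day of study drug administration in Period II for those who received placebo in Period I and transitioned to Period II".

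On the gap itself, Protocol 8.2 states "Non-dosing period is defined as maximum 4 weeks from Week 52 or ET Week 28 to Day 1 of Period III", and Protocol 8.6.1 gives no study drug in it. The same section 8.2 sets a follow-up rule "for subjects who withdraw from the Non-dosing period before ND Week 2" and states that there is no follow-up for those who withdraw at ND Week 2 or later. Protocol 11.8.1 and 11.9.1 also deal with subjects who withdraw in this period.

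The formula feeds the exposure summary in SAP 10.1 and the classes in SAP 10.2 under "Duration of treatment (R788 treatment period", where the two highest classes are 24 to below 52 weeks and 52 weeks or more.

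**The concern.** Taking the Non-dosing period off a first-to-last-dose span is correct only if that period lies inside the span, which requires a dose after it. A subject who withdraws during the Non-dosing period has no such dose. The span already ends with Period II, so the subtraction deletes treated days.

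The error has one direction: exposure is understated. It can also make the SAP report two different durations for the same doses in the same subject, one from the R788-treatment-period formula and one from the Period II or long-term formula. At stake is the accuracy of a descriptive account of how long R788 was taken, in a study planned for 24 subjects. If all 24 receive R788, each subject is 1/24 = 4.2 percentage points of the class table.

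**Working it through.** The documents state no exposure figure to reproduce, so the check applies the SAP formula to nominal day counts.

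**Inputs**

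- R788 subject completing Period II: dosed Days 1 to 365 (Week 52 target day 7 × 52 + 1, SAP 5.9).
- Period I placebo subject: R788 only in Period II, nominally 197 days. Protocol 8.2 gives "Period II is defined as 28 weeks from ET Day 1 to ET Week 28", and the target day is 7 × 28 + 1 = 197. Weeks 24 to 52 for completers give the same count: 365 − 169 + 1 = 197.
- R788 early-transition subject, assuming transition at Week 12 (Day 85): last dose on Day 85 + 196 = 281. Later transition gives longer exposure and a smaller percentage.
- Non-dosing Day 1 is the Week 52 or ET Week 28 visit (SAP 5.9 item 4). Withdrawal at Non-dosing Day 15 makes end − start = 14. At the 4-week limit (Day 29) it is 28.
- It is assumed that the last dose falls on the day of the final Period II visit and that the end day is the day of withdrawal.

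**Formula**

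Reported exposure = (last − first + 1) − (end − start). Days actually on R788 for a subject who does not restart = last − first + 1. Proportion lost = (end − start) / (last − first + 1).

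| Subject | Days on R788 | Reported, withdrawal at Day 15 | Reported, 4-week limit |
|---|---|---|---|
| R788 completer | 365 | 365 − 14 = 351 (3.8% lost) | 365 − 28 = 337 (7.7%) |
| R788 early transition at Week 12 (assumed) | 281 | 281 − 14 = 267 (5.0%) | 281 − 28 = 253 (10.0%) |
| Period I placebo subject | 197 | 197 − 14 = 183 (7.1%) | 197 − 28 = 169 (14.2%) |

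**Agreement with the neighbouring formulas**

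At the 4-week limit, the long-term formula gives the R788 completer 365 days and the R788-treatment-period formula gives 337. The Period II formula gives the placebo subject 197 days and the R788-treatment-period formula gives 169.

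**Effect on the exposure classes**

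The 52-week cut is 52 × 7 = 364 days. The nominal completer moves from 365 days (52.1 weeks) to 351 (50.1 weeks) or 337 (48.1 weeks), one class down in both cases. The Week 52 visit window is Days 358 to 372. At the top of it, withdrawal on the earliest ND Week 2 day (Day 12) still gives 372 − 11 = 361, below 364. A completer whose last dose falls on Days 358 to 363 is below the cut with no subtraction, so the shift applies only to those with at least 364 days.

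**Visit windows**

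For a placebo subject who completed Period I, R788 can run from Day 172 to Day 358 (187 days) or from Day 166 to Day 372 (207 days). With 28 days subtracted the loss is 28/187 = 15.0% or 28/207 = 13.5%, around the nominal 14.2%.

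**Check for subjects who restart**

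Take R788 on Days 1 to 197 and, as an illustration, again on Days 225 to 336. Days on drug: 197 + 112 = 309. The formula gives 336 − (225 − 197) = 308, or 336 − (224 − 197) = 309, depending on which day is taken as the end. For restarters it is right to within a day.

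**The case against.** The strongest reply is that this is an unstated condition rather than a wrong rule. The protocol's Non-dosing period ends at Day 1 of Period III. A subject who withdraws has no such day, so the end day is undefined, and the term is already meaningless for anyone who skipped the period or never entered it. A sensible programmer would set it to zero in all these cases. It is true that the end day is not spelled out. But SAP 10.1 and 10.2 require a Non-dosing duration, classed as below or at least 4 weeks, for the Non-dosing group, which SAP section 3 defines as those who transitioned to that period. Withdrawers therefore must be given an end day, and once they have one the formula applies to them as written. The same list in section 7 also splits the long-term formula by whether Period I was discontinued, so conditions are written where they are meant.

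Other points on that side stand:

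- **Size.** A reader might infer that affected subjects typically lose about 14%. The documents do not support that. The figure needs a Period I placebo subject who stays off drug to the 4-week limit and then does not restart. Protocol 8.5 sends those who complete the Non-dosing period, and those who receive rescue therapy in it, to Period III. Entrants have also already consented to Period III (Protocol 8.4).
- **Number affected.** It equals the number who withdraw during the Non-dosing period, plus any not restarted at a data cutoff to whom the term is applied. Neither is given, and either may be zero.
- **Reach.** A reader might infer that safety rates or efficacy are distorted. SAP 12.1 bases incidence on subject counts, not person-time. Average daily dose weights by time at each dose, and no efficacy analysis uses this variable.
- **Redundancy.** The Period II and long-term formulas would still report the full span for many of the same subjects.

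**Conclusion.** The point holds. As written, the formula understates R788 exposure for any subject who withdraws during the Non-dosing period, by the number of days between its start and the assigned end day. At nominal timing that is 3.8% (R788 completer) to 7.1% (Period I placebo subject) at Day 15, and 7.7% to 14.2% at the 4-week limit. A completer with at least 364 days can fall from the top exposure class into the one below, and the result contradicts the SAP's own Period II or long-term figure for the same doses.

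The effect is confined to the descriptive outputs of SAP 10.1 and 10.2, and whether any subject is affected cannot be told from the documents. The day counts assume nominal visit days, a last dose on the final Period II visit day and an end day equal to the day of withdrawal. The correction is worth making because the rule is wrong for a group that the protocol foresees, and it costs almost nothing.

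**What to change.** In SAP section 7, make the R788-treatment-period formula conditional:

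- Subjects given R788 in Period III after a Non-dosing period: last − first + 1 − (end − start of the Non-dosing period).
- All others: last − first + 1, with the Non-dosing term set to zero. This covers subjects who withdrew during the Non-dosing period, skipped it, never entered it, or had not restarted R788 at the data cutoff.

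In the same sentence, state which days count as the start and end of the Non-dosing period, including the end day for withdrawers. That also removes the one-day ambiguity for restarters.

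Summing the durations of Periods I to III might look like an equivalent remedy, but it is not. It would count Period I placebo time as R788. It can count the Week 24 day twice when the last Period I dose and the first Period II dose fall on the same day. It can also differ from the span for early-transition subjects, whose ET Day 1 may fall up to 1 week after the last Period I visit (Protocol 11.5.1).

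The cost is one clause in the SAP and one line of code, with no change to conduct or data collection.

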### **12.1.5 Early occurrence of adverse events and adverse drug reactions**

Applicable period: Period I, R788 treatment period

The variables to be analyzed are as follows:

- AEs and ADRs occurring up to Week 4 (Day 29)
- AEs and ADRs of interest occurring up to Week 4 (Day 29)
- AEs and ADRs occurring up to Week 12 (Day 85)
- AEs and ADRs of interest occurring up to Week 12 (Day 85)

The number of events, number of subjects with events, and incidence rates of events will be presented overall and by primary SOC and PT.

For AEs and ADRs of interest, event categories will be presented instead of primary SOCs.

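### The response-duration rule counts the day response fails as a response day, so a subject who fails exactly 84 days after the start meets the 85-day criterion for sustained response

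*SAP*

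**What the plan says.** SAP section 7 gives one formula: "Duration of platelet response = End day of response – Start day of response + 1". The plus one makes the count inclusive at both ends. The end day is then set in three ways.

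- **Rescue:** "The end day of response is defined as the day of use of a rescue medication".
- **Loss of count:** the end day is "the first day of the period in which the platelet count fell below" 50000/µL, provided the low period lasts 28 days or more. The earlier of this day and the rescue day applies.
- **Still responding when the period ends or the subject leaves it:** "the last measurement day in each period is defined as the end day of response".

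The same section then sets the criterion for sustained stable platelet response: "Maintenance of the platelet count for the subsequent 12 weeks is defined as platelet response for at least 12 weeks (85 days". The response must begin within 12 weeks of starting treatment. SAP section 11.2.3.1 compares the rate of this endpoint between Periods I and II by McNemar test, in subjects who received placebo in Period I and moved to Period II.

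**The concern.** An inclusive day count is right only if the last day counted is a day in response. That holds for a response still present at the end of the period, where the last measurement is at or above 50000/µL. It does not hold for a lost response, where the last day counted is the day of the first low count or of rescue.

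The extra day matters because the criterion is 85 inclusive days and the visits are spaced so that the 85th day is itself a scheduled visit. At that visit the rule cannot tell a subject who has kept the response from one who has lost it. Both score 85 and both are called sustained responders. At stake are the classification of subjects in the endpoint tested by McNemar and a one-day excess in the durations summarised in SAP sections 11.2.1.3, 11.2.2.2, 11.2.3.3 and 11.2.6.2.

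**Working it through.** **Inputs**

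- Duration formula, end-day rules and the 85-day criterion: SAP section 7.
- Platelet visits every 2 weeks in Period I and every 4 weeks in Period II: SAP section 5.9.
- Day of a visit at week x: 7x + 1, from the time-window tables in SAP section 5.9. For Period II, days are counted here from the first day of Period II dosing.
- Planned placebo subjects, 8: Protocol section 8.9.1.

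**Reproducing the plan's 85 days.** For a response starting on day S and still present 12 weeks later, on S + 84, duration = (S + 84) − S + 1 = 85. This matches the SAP's figure, and SAP section 12.1.5 likewise places Week 12 at Day 85. The 85 therefore presupposes that S + 84 is a day in response.

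**Applying the loss rule at the same point.** Let the first count below 50000/µL fall on S + 84 and the low period last at least 28 days. The end day is S + 84, so duration = (S + 84) − S + 1 = 85, and the subject is a responder. Rescue on S + 84 gives the same result.

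**On scheduled visits**

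| Period | Response starts | First low count | Days from first low count to period end |
|---|---|---|---|
| I | Weeks 2, 4, 6, 8 | Weeks 14, 16, 18, 20 | 70, 56, 42, 28 |
| II | Weeks 4, 8, 12 | Weeks 16, 20, 24 | 84, 56, 28 |

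Every row leaves room for the 28-day low period, and every row scores 85. Two examples:

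- Period I: high at Weeks 8 to 18, low at Weeks 20 to 24. Start Day 57, end Day 141, 141 − 57 + 1 = 85.
- Period II: high at Weeks 4, 8 and 12, low from Week 16. Start Day 29, end Day 113, 113 − 29 + 1 = 85.

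Period I starts at Weeks 10 and 12 are left out of the table because only 14 and 0 days remain after the 12-week visit. A 28-day low period cannot then be shown within the period, and the text does not clearly set an end day. That is a separate gap.

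**With the failure day excluded.** The end day becomes S + 83 and duration = (S + 83) − S + 1 = 84, which is below 85: non-responder.

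**How many subjects sit on the boundary.** Only a lost response with exactly 84 days from start to failure changes class. At 83 days or fewer the subject fails either way; at 85 or more the subject passes either way. If all visits fall on nominal days, everyone first found low at the 12-week visit is affected. If instead both visit days are assumed independent and uniform within their windows, the share with exactly 84 days is 1/7 = 14% in Period I (±3 days) and 1/15 = 7% in Period II (±7 days).

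**Weight of one subject.** With 8 placebo subjects, one reclassification moves a rate by 1/8 = 12.5 percentage points. The overseas extension study reported 10/44 = 22.7% for this kind of response (Protocol section 1.3.2.2), which corresponds to 8 × 0.227 = 1.8 subjects here. Assuming no sustained responders in Period I, the exact McNemar p-value with k responders in Period II is 2 × 0.5^k, capped at 1: 1.0 for k = 1 and 0.5 for k = 2. It passes 0.05 only between k = 5 (0.063) and k = 6 (0.031).

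**The case against.** The strongest defence is that S to S + 83 is 84 days, a full 12 weeks with no failure observed, so calling this 12 weeks maintained is reasonable. It would be, if the criterion were 84 days. The SAP requires 85 inclusive days, and for these subjects the 85th is the day of failure.

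It can also be said that dating a loss at its first documented low count is ordinary practice, and that ending an ongoing response at the last measurement is the usual distinction between an event and a censored observation. This stands. It is the reason the fault is one day and no more.

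A reader might infer more from the text, in three ways that the documents do not support.

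- **That the rule credits a whole visit interval (14 or 28 days) of unearned response.** This takes the last high count as the true end of response. Counts are known only at visits, and the loss could have occurred on any day up to the first low count.
- **That subjects who lose response are favoured over subjects who keep it.** Take a subject who responds from Week 12 and leaves after Week 22 still responding. The score is 155 − 85 + 1 = 71 days, so the subject is a non-responder. That subject was not observed for 12 weeks, and SAP section 7 makes those who cannot be assessed because of discontinuation non-responders. The loss rule plays no part.
- **That a lost response should end at the last high count.** That is a different convention. It could shorten true responses, and Protocol section 4.1.2 chose these endpoints for comparison with the overseas studies, whose end-day rule the documents do not give.

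The endpoint's low standing also counts against the point: SAP section 6.5.2 treats every variable other than the primary endpoint as for reference only.

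**Conclusion.** The rule is wrong as written, by one day. A day of failure is counted as a day of response whenever a response ends through low counts or rescue. A subject who fails exactly 84 days after the start is therefore classed as a sustained responder. No other section of the SAP excludes the failure day or requires a count at or above 50000/µL at the 12-week point.

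The practical effect is small. It is limited to boundary cases in a reference-only secondary endpoint with about 8 planned placebo subjects, and to a one-day excess in summaries of lost responses. At the overseas rate, a single reclassification would not carry the McNemar test across 5%. The primary endpoint counts visits from Weeks 14 to 24 and does not use this rule.

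The conclusion rests on one inference: that the platelet response named in the 85-day criterion is measured by the duration formula just above it in SAP section 7. That is the only day-count definition the SAP gives. The share of subjects affected depends on how closely visits keep to their nominal days, which the documents cannot settle. Section 7 also brings unscheduled and out-of-window measurements into the duration.

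**What to change.** In SAP section 7, state that a response lost to low counts ends on the day before the first count of the qualifying low period, and that a response ended by rescue ends on the day before rescue. Omitting the plus one for lost responses gives the same durations. State also that sustained stable platelet response uses this duration. Leave the rule for responses still present at period end as it is.

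The cost is one sentence and one derivation line. Durations of lost responses become one day shorter. If the end day itself is moved, the end-of-maintenance marker in the swimmer plots (SAP section 11.2.1.6) moves by a day too; omitting the plus one leaves it in place. If outputs already exist, the only subjects who can change class are those with a lost response scored at exactly 85 days, so a short listing would show whether any result is affected.
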